Pharmacokinetic Modeling of Ropivacaine Following Single Shot Erector Spinae Plane Block in Anesthetized Children

NCT: 04298099

Date: 1/20/2021 (original protocol document date)

Protocol

This pilot study was a prospective, observational investigation approved by the Baylor College of Medicine IRB (H-4638). In compliance with the EQUATOR network, all reporting was conducted under the STROBE guidelines. Written informed consent (with assent where applicable) was obtained by the parent(s) or legal guardian(s) for all enrolled participants. Eligibility criteria included patients aged 6 months to 18 years weighing more than 4kg, scheduled to undergo minimally invasive video-assisted thoracoscopic surgery at Texas Children's Hospital. Exclusion criteria included allergy to local anesthetics, liver or renal dysfunction, pre-existing hypoalbuminemia, tumor or infection/abscess at the injection site, and a BMI $> 95^{\text{th}}$ percentile.

Patients received an inhalational or intravenous induction with a general endotracheal tube anesthesia at the discretion of the attending anesthesiologist. After the airway was secured, patients were placed in the lateral decubitus position and a single-shot unilateral ultrasound-guided ESP block, as all the procedures were unilateral incisions, was performed as previously described 1-2 dermatomal levels above the surgical incision site.⁷ All patients received Ropivacaine 0.5% at 0.3ml/kg (1.5mg/kg) in the fascial plane deep to the erector spinae muscle. Since there are no standardized dosing guidelines for ESP blocks in children, we chose a slightly higher dose from the previously published Ropivacaine dosing for TAP blocks of 0.25-0.75mg/kg but remaining within the consensus maximum dosing of 1.5mg/kg for peripheral nerve blocks.^{2,8} Post-anesthesia care unit (PACU) dermatomal assessments to ice were performed to validate ESP block accuracy. Intraoperative morphine equivalents (mg/kg) were additionally collected. Total and free serum Ropivacaine concentrations were obtained at baseline and the following time point after block

injection: 30, 60, and 90-minutes and 2, 4, and 6-hours. These time-points reflect those previously noted in the literature, recognizing that serum capture of Ropivacaine is likely undetectable beyond 6-hours.⁸⁻¹⁰ A baseline alpha-1 acid glycoprotein (AAG) was also collected.

Samples were centrifuged for 15-minutes at 1100G within 2-hours of collection and the plasma was frozen at -80°C for processing at Lab ExperTox Inc. We applied the same laboratory analysis as previously described, demonstrating the reproducibility of total and free Ropivacaine levels with liquid chromatography/mass spectroscopy (LC-MS/MS).⁸⁻¹² The LC-MS/MS analysis was performed with the Agilent Technologies 6460 mass spectrometer connected with the Agilent 1200 series HPLC system via electrospray ionization mode. The samples were analyzed in positive ionization mode with the voltage set at 3000V. Data acquisition and data analysis were performed with the Agilent Mass Hunter software (Version B.07.00). The total Ropivacaine concentrations were measured after protein precipitation in methanol. The free Ropivacaine concentrations were measured with the same technique after ultracentrifugation of the samples with Vivaspin 2, 10 KDa molecular weight cut-off Concentrators (GE Healthcare, UK). The assay was validated by spiking negative serum with known concentrations of Ropivacaine. The assay method was linear over the concentration range 5 -3000 ng/mL, with a limit of detection of 1 ng/mL and a limit of quantification of 5 ng/ml.

REFERENCES:

4. Suresh S, De Oliveira GS Jr. Local anaesthetic dosage of peripheral nerve blocks in children: analysis of 40 121 blocks from the Pediatric Regional Anesthesia Network database. *Br J Anaesth.* 2018; 120(2):317-322.
5. L Long JB, Birmingham PK, De Oliveira GS Jr, et al. Transversus abdominis plane block in children: a multicenter safety analysis of 1994 cases from the PRAN (Pediatric Regional Anesthesia Network) database. *Anesth Analg.* 2014; 119(2):395-9.

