Pharmacokinetic Modeling of Ropivacaine Following Single Shot Erector Spinae Plane Block in Anesthetized Children

NCT: 04298099

Date: 2/17/2021 (date of original analysis document)

Statistical Analysis:

Prior investigations have suggested that a 1-compartment model with an absorption rate constant best describes the pharmacokinetic profile of Ropivacaine.^{12,13} Therefore, population pharmacokinetic analysis was performed with NONMEM v.7.4^{12,13} (Icon, PLC; Dublin, Ireland) and PDx-Pop 5.2 (Icon, PLC, Dublin, Ireland) using first-order conditional estimation with interaction (FOCE-I). One- and two-compartment models with an absorption rate constant (K_a^{-1}) and various error structures were evaluated, and the final model was selected based upon a significant reduction in the objective function value ($p<0.05$), in conjunction with standard subjective evaluation of graphical representations of model fit. Models were generated for both total and free Ropivacaine concentrations. After the final models were generated, simulation ($n=1000$) of serum concentrations (total and free Ropivacaine) was performed using 1, 1.5, 2, and 2.5 mg/kg/dose in a patient with a median weight value from the dataset.

REFERENCES:

4. Suresh S, De Oliveira GS Jr. Local anaesthetic dosage of peripheral nerve blocks in children: analysis of 40 121 blocks from the Pediatric Regional Anesthesia Network database. *Br J Anaesth.* 2018; 120(2):317-322.
5. L Long JB, Birmingham PK, De Oliveira GS Jr, et al. Transversus abdominis plane block in children: a multicenter safety analysis of 1994 cases from the PRAN (Pediatric Regional Anesthesia Network) database. *Anesth Analg.* 2014; 119(2):395-9.

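### Should a blood draw be moved past 6 hours because total ropivacaine is probably still measurable then?

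*Protocol*

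**What the plan says.** The Protocol's sampling paragraph schedules a baseline draw and six draws after the block, at "30, 60, and 90-minutes and 2, 4, and 6-hours". It gives two reasons: the times follow earlier literature, and sampling stops at 6 hours "recognizing that serum capture of Ropivacaine is likely undetectable beyond 6-hours". The sentence carries references 8 to 10. The dose is 1.5 mg/kg. Total and free drug are both measured, by an assay "with a limit of detection of 1 ng/mL and a limit of quantification of 5 ng/ml". Processing is time-limited: "Samples were centrifuged for 15-minutes at 1100G within 2-hours of collection".

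The SAP's Statistical Analysis section evaluates "One- and two-compartment models with an absorption rate constant" and states that "Models were generated for both total and free Ropivacaine concentrations". Simulation "of serum concentrations (total and free Ropivacaine) was performed using 1, 1.5, 2, and 2.5 mg/kg/dose" follows, for a child of median weight. No time span is given for the simulated profiles. Neither document states an expected half-life, clearance, volume or free fraction.

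**The concern.** The claim about 6 hours does not separate total from free drug, and nothing in the documents derives it. By title, its references concern bupivacaine in neonates, levobupivacaine, and unbound ropivacaine during an epidural infusion of 24 to 72 hours. None of these titles is about total ropivacaine after a single injection. Set against the Protocol's own dose and assay limits, the claim seems to require implausibly fast elimination of total drug.

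If total drug persists, a schedule with four of its six post-block draws in the first 2 hours and none after 6 hours sees little of the terminal phase. Clearance, half-life and any simulated concentration after 6 hours would then be less precise than the same number of draws could make them. Moving the 90-minute draw to 10 to 12 hours looks like a cheap gain.

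**Working it through.** **Inputs from the documents.** Dose: 0.5% is 5 mg/mL, and 5 × 0.3 mL/kg = 1.5 mg/kg, which agrees with the Protocol. Detection limit 1 ng/mL, quantification limit (LOQ) 5 ng/mL. Draws at 0.5, 1, 1.5, 2, 4 and 6 h. The 6-hour figure itself cannot be reproduced, because no pharmacokinetic value is stated. Every volume (V/F), half-life (T), absorption rate (ka), free fraction, variability and sample size below is an assumption.

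**Step 1: what the 6-hour claim requires.** With one compartment and instant absorption, C(t) = (1500/V) × 2^(−t/T) ng/mL. Setting C(6 h) equal to the limit gives T = 360 / log2[(1500/V)/limit] minutes. For V = 1 L/kg and the LOQ: 360 / log2(300) = 360/8.23 = 44 min.

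| V/F (L/kg) | 0.5 | 1 | 2 | 5 | 10 |
|---|---|---|---|---|---|
| Half-life below which total is under LOQ at 6 h (min) | 39 | 44 | 50 | 61 | 73 |
| Same, under detection limit (min) | 31 | 34 | 38 | 44 | 50 |

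With ka 1.5/h the LOQ row becomes 30, 35, 41, 51 and 63 min. If the claim is read as referring to a draw at 12 h, the instant-absorption LOQ bounds double to 78 to 147 min.

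For free drug at 5 to 10% of total and V/F 1 to 5 L/kg, the LOQ bound at 6 h is 1.2 to 3.8 h. The claim is therefore doubtful for total drug and credible for free drug.

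**Step 2: how much of the curve is unseen.** With k = ln 2/T, the share of AUC beyond 6 h is (ka·e^(−6k) − k·e^(−6ka))/(ka − k). For T = 3 h and ka = 1/h: (0.250 − 0.0006)/0.769 = 32%. Over ka 1 to 6/h the share is 2–5% at T = 1 h, 13–19% at 2 h, 26–32% at 3 h and 51–56% at 6 h.

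**Step 3: what the swap buys for total drug.** First-order population information matrix, one compartment, V/F 2 L/kg, ka 1.5/h, 20 children, between-subject SD 50% on ka and 30% on clearance and volume, 20% residual error. The table gives relative standard errors (%), as plan → 90-minute draw moved to 12 h in all children.

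| Half-life | Clearance | Half-life | Cmax |
|---|---|---|---|
| 3 h | 7.7 → 7.0 | 13.0 → 9.9 | 6.4 → 6.4 |
| 4 h | 8.9 → 7.0 | 14.8 → 10.3 | 6.5 → 6.4 |
| 6 h | 12.6 → 7.4 | 19.1 → 11.1 | 6.6 → 6.5 |

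With ka 3/h the clearance gains shrink to 7.4 → 7.0, 8.1 → 7.0 and 10.3 → 7.3. At a 2-hour half-life clearance is 7.0 either way. At 1 hour the 12-hour total concentration is about 0.3 ng/mL, so the draw is lost: clearance goes from 7.0 to 7.1 and volume from 8.6 to 9.0.

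**Step 4: what it costs for free drug.** Free fraction 5%, ka 1.5/h, 20% plus 1 ng/mL error, values under 5 ng/mL dropped. The typical 12-hour concentration is 0.8 ng/mL at a 2-hour half-life and 2.8 at 3 hours, so the moved draw is lost in both.

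| Half-life | ka | Volume |
|---|---|---|
| 1 h | 69 → 85 | 56 → 69 |
| 2 h | 16.6 → 17.0 | 9.2 → 9.8 |
| 3 h | 16.8 → 17.3 | 9.3 → 9.9 |

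At 4 hours and above the free draw is measurable (5.3 ng/mL at 4 h) and the swap helps: clearance 9.1 → 7.2 at 4 h and 12.9 → 7.5 at 6 h. Across 24 assumed free-drug cases (fraction 3, 5 or 10%; ka 1.5 or 3/h; half-life 2 to 6 h), the 12-hour sample is under the LOQ in 13.

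**The case for a change.** The best case for changing the plan is that the gains are larger and sturdier than the 3-hour row suggests. If half the children end up with neither the 90-minute nor the 12-hour sample, clearance is still 7.2/7.6/8.9% at half-lives of 3/4/6 h, better than the plan's 7.7/8.9/12.6%. In 36 two-compartment runs, clearance and terminal half-life improved every time; in one set with a 6-hour terminal half-life, clearance went from 28.5% to 7.5%. Correcting the sentence about 6 hours would cost almost nothing.

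The criticism of the stated reason stands, with two limits. The sentence is cited, and the cited papers cannot be read here. Its wording is also hedged, and Step 1 shows that reading it as a later time narrows the gap, though it would still fail at a 3-hour half-life.

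The argument for redesign does not carry. In the two-compartment example ka has a standard error of 45% or more, so those runs show direction only. The large one-compartment gains need half-lives near 6 hours. An equal number of draws is not an equal burden: a 10-to-12-hour draw needs access to the child and processing within 2 hours at a later time of day, and the documents do not describe line access or length of stay. Children who stay long enough may also differ in age or illness from those who leave, which the calculations ignore. The draw given up lies at the typical peak in the base case: ln(1.5/0.231)/(1.5 − 0.231) = 1.47 h, or 88 min, although population Cmax precision hardly suffers.

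**Conclusion.** No change to the plan follows. The reason given for stopping at 6 hours is poorly supported for total drug: it needs a half-life below roughly 1 hour (39 to 73 min over the assumed volumes). But no analysis in the SAP depends on that sentence. The models are fitted to whatever concentrations were measured.

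The schedule is a fair trade-off. Early draws serve absorption and the peak for both analytes. A late draw would serve clearance and the terminal phase of total drug if its half-life is about 3 hours or more, by 0.4 to 0.7 percentage points of clearance standard error at 3 hours and 3.0 to 5.2 points at 6 hours. It would harm free-drug estimates where it falls under the LOQ. The documents name no half-life or AUC endpoint, no precision target and no simulation horizon, so no stated aim is shown to suffer. The Protocol calls this a pilot, and both documents describe the work as done, so the draw probably can no longer be moved.

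What remains is ordinary reporting practice: a total-drug half-life, an AUC to infinity or a simulated concentration past 6 hours is an extrapolation and would be described as one. That alters no result the plan promises. The conclusion rests on the assumed pharmacokinetic values; a known long half-life, with terminal-phase estimates as a stated aim, would make a draw after 6 hours worth considering in a later study.

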Pharmacokinetic Modeling of Ropivacaine Following Single Shot Erector Spinae Plane Block in Anesthetized Children

NCT: 04298099

Date: 2/17/2021 (date of original analysis document)

Statistical Analysis:

Prior investigations have suggested that a 1-compartment model with an absorption rate constant best describes the pharmacokinetic profile of Ropivacaine.^{12,13} Therefore, population pharmacokinetic analysis was performed with NONMEM v.7.4^{12,13} (Icon, PLC; Dublin, Ireland) and PDx-Pop 5.2 (Icon, PLC, Dublin, Ireland) using first-order conditional estimation with interaction (FOCE-I). One- and two-compartment models with an absorption rate constant (K_a^{-1}) and various error structures were evaluated, and the final model was selected based upon a significant reduction in the objective function value ($p<0.05$), in conjunction with standard subjective evaluation of graphical representations of model fit. Models were generated for both total and free Ropivacaine concentrations. After the final models were generated, simulation ($n=1000$) of serum concentrations (total and free Ropivacaine) was performed using 1, 1.5, 2, and 2.5 mg/kg/dose in a patient with a median weight value from the dataset.

REFERENCES:

4. Suresh S, De Oliveira GS Jr. Local anaesthetic dosage of peripheral nerve blocks in children: analysis of 40 121 blocks from the Pediatric Regional Anesthesia Network database. *Br J Anaesth.* 2018; 120(2):317-322.
5. L Long JB, Birmingham PK, De Oliveira GS Jr, et al. Transversus abdominis plane block in children: a multicenter safety analysis of 1994 cases from the PRAN (Pediatric Regional Anesthesia Network) database. *Anesth Analg.* 2014; 119(2):395-9.

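### Does the SAP need to name its residual-error candidates and say how non-nested models were ranked?

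*SAP*

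**What the plan says.** The whole rule stands in the SAP's Statistical Analysis section. The structural candidates are named: "One- and two-compartment models with an absorption rate constant". The residual-error candidates are not. Estimation is by first-order conditional estimation with interaction in NONMEM.

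One criterion covers both choices: "and various error structures were evaluated, and the final model was selected based upon a significant reduction in the objective function value", at p<0.05, applied "in conjunction with standard subjective evaluation of graphical representations of model fit". It is used twice, because "Models were generated for both total and free Ropivacaine concentrations". The chosen models then feed the dose simulations: "After the final models were generated, simulation ($n=1000$) of serum concentrations (total and free Ropivacaine) was performed", at 1, 1.5, 2 and 2.5 mg/kg for a patient of median weight.

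The section gives no OFV cut-off, degrees of freedom or information criterion, and it does not say whether residual error was added to the simulated concentrations. The Protocol calls the study a pilot, prospective and observational, and gives every child 1.5 mg/kg.

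**The concern.** A p-value for an OFV difference needs nested models. One against two compartments is nested. Additive against proportional residual error is not: each has one residual parameter and neither contains the other. If those two were among the error structures and were compared directly, p<0.05 has no meaning for that pair. The only stated criterion left is then a graphical review that the SAP itself calls subjective.

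Even for nested steps, p<0.05 stands for different OFV drops depending on what is added. A reader who does not know the candidates cannot re-run the selection for either analyte.

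The selected model is also used beyond the observed dose, up to 2.5 mg/kg. Proportional error grows with concentration and additive error does not, so the choice could affect the width of the simulated ranges.

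**Working it through.** **Inputs.** From the SAP: p<0.05, the one- and two-compartment candidates, unnamed error structures, and simulated doses of 1, 1.5, 2 and 2.5 mg/kg. From the Protocol: a single administered dose of 1.5 mg/kg. The documents give no OFV value or cut-off, so there is no figure of the plan's own to reproduce.

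**1. Nested steps.** The OFV drop is referred to a chi-square distribution with degrees of freedom equal to the number of added parameters. Nominal 5% cut-offs:

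| Step | Reference | OFV drop |
|---|---|---|
| Additive or proportional to combined error | chi-square, 1 df | 3.84 |
| Same, allowing for a variance of zero under the null | 50:50 mixture of 0 and 1 df | 2.71 |
| One to two compartments (intercompartmental clearance, peripheral volume) | chi-square, 2 df | 5.99 |
| Same, plus one between-child variance | chi-square, 3 df | 7.81 |

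Using 3.84 for the 2-df step would give a nominal size of P(chi-square on 2 df > 3.84) = 14.7% instead of 5%. Nothing in the SAP says this was done; it states a p-value, not a fixed drop of 3.84.

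The compartment figures are nominal only. Zero intercompartmental clearance lies on the edge of the parameter space and leaves the peripheral volume unidentified, so neither a plain chi-square nor a simple mixture is assured there. A printed table of degrees of freedom would therefore suggest more exactness than the test has.

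**2. The non-nested pair.** AIC = OFV + 2k and BIC = OFV + k·ln(n), up to a constant. With equal k the penalties cancel:

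AIC(additive) − AIC(proportional) = OFV(additive) − OFV(proportional), and the same for BIC.

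So the formal remedy is to choose the lower OFV. Suppose instead that an analyst had wrongly demanded a drop of 3.84 before switching. The two rules would then disagree only when the OFVs differ by less than 3.84, that is, at a likelihood ratio below exp(3.84/2) = exp(1.92) = 6.8. In that range the data separate the two models weakly. The nested route, testing each against combined error, is also open.

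**3. Possible effect on the simulations.** With linear kinetics, proportional residual SD relative to its value at 1.5 mg/kg is 1/1.5 = 0.67, 1, 2/1.5 = 1.33 and 2.5/1.5 = 1.67 at the four doses. Additive SD stays at 1 throughout.

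Assume a between-child CV *i* of 20% to 40% and a residual SD *r* of 10% to 30% of the peak at 1.5 mg/kg, equal under both models at that dose. None of these values is in the documents. At 2.5 mg/kg the additive SD relative to the peak is r × 1.5/2.5 = 0.6r. The ratio of 97.5th percentiles, proportional to additive, under a normal approximation is

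[1 + 1.96·√(i² + r²)] / [1 + 1.96·√(i² + (0.6r)²)]

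- i = 0.3, r = 0.2: 1.707/1.633, or +4.5%
- i = 0.4, r = 0.1: 1.808/1.793, or +0.9%
- i = 0.2, r = 0.3: 1.707/1.527, or +11.7%

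Repeating the grid by simulation, with log-normal between-child variation and residual error applied to each child's own prediction, gives about +2% to +16%, and about +8% in the central case. The size depends on the assumed form. Either range applies only if residual error entered the simulations and if the choice really lay between these two structures.

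**The case for a change.** The strongest case for acting is that this is the SAP, and a selection rule that another analyst cannot re-run falls short of what a SAP is for. Degrees of freedom follow from parameter counts only when the models are listed, and the error models and random effects are not. Where the p-value is undefined, what remains is judgement. The repair would be two or three sentences and would need no new data.

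Part of this stands. The error candidates are unnamed, no ranking rule for non-nested pairs is given, and the possible effect on the simulated upper percentiles is not zero. A reader of the eventual report would be helped by a list of the error models tried and a note on whether residual error was simulated.

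It does not amount to a defect in the analysis. That additive and proportional error were compared directly is a supposition. The structural candidates, the estimation method and the significance level are all stated. A likelihood ratio test with diagnostic plots is a sound way to choose among these models, and the plots can inform a choice that no p-value settles. Writing the rule out would record what a competent analyst would do anyway. The SAP is also in the past tense, so added wording would describe the selection, not govern it.

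**Conclusion.** No change to the plan. The SAP leaves a gap that analysts fill sensibly: the likelihood ratio test where models are nested, and the lower OFV with diagnostic plots, or a test of each against combined error, where they are not. Neither document shows an invalid comparison, a wrong cut-off, or a final model, clearance or absorption constant that would differ. The 1% to 16% range is conditional on assumed variabilities and on two unstated choices, so it bounds a possibility and does not measure an error. No confirmatory test or error rate is at stake in this pilot observational study.

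The conclusion assumes that the error candidates were fitted to the same concentrations on the same scale, so that their OFVs are comparable, and that p<0.05 was read with the degrees of freedom appropriate to each nested step. Nothing in the documents contradicts either assumption.
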